#### 4.6.2.2.2. Hypoglycemic Events derived from CGM

Level 2, Level 2 ending with BG value  $\geq 70$  mg/dL, and Level 1 or Level 2 hypoglycemic events collected from the sponsor provided CGM are defined in Appendix 6, Section 6.6.2. The analysis for incidence, event rate, and duration are described in the table below. All data are included in the analysis. Missing data will be handled as described in Appendix 6.

Endpoint	CGM Session*	Statistical Method
Event rate of Level 1 or Level 2 hypoglycemic events (events/participant/year): 
 
• 24-hour
 
	Baseline, 0-4, 8-12, 22-26, 0-26 weeks, post-treatment period	Negative binomial regression with treatment, baseline HbA1c and baseline Level 1 or Level 2 hypoglycemia rate as covariates, log (exposure/365.25 days) as the offset in the model.
Event rate of Level 2 hypoglycemic events (events/participant/year): 
 
• 24-hour
 
	Baseline, 0-4, 8-12, 22-26, 0-26 weeks, post-treatment period	Negative binomial regression with treatment, baseline HbA1c and baseline Level 2 hypoglycemia rate as covariates, log (exposure/365.25 days) as the offset in the model.

Endpoint	CGM Session*	Statistical Method
Event rate of Level 2 hypoglycemic events ending with $\geq 70$ mg/dL (events/participant/year): • 24-hour	Baseline, 0-4, 8-12, 22-26, 0-26 weeks, post-treatment period	Negative binomial regression with treatment, baseline HbA1c and baseline rate for Level 2 hypoglycemia ending with $\geq 70$ mg/dL as covariates, log (exposure/365.25 days) as the offset in the model.
Incidence of Level 1 or Level 2 hypoglycemic events: • 24-hour	Baseline, 0-4, 8-12, 22-26, 0-26 weeks, post-treatment period	Logistic regression with treatment, baseline HbA1c and baseline Level 1 or Level 2 hypoglycemia rate as covariates.  The total number of episodes, number of episodes that includes Level 2 hypoglycemia episodes, and number of episodes that include glucose readings $<54$ mg/dL(3.0 mmol/L) but no Level 2 hypoglycemia episodes will be summarized for each CGM session.
Incidence of Level 2 hypoglycemic events: • 24-hour	Baseline, 0-4, 8-12, 22-26, 0-26 weeks, post-treatment period	Logistic regression with treatment, baseline HbA1c and baseline Level 2 hypoglycemia incidence as covariates.
Incidence of Level 2 hypoglycemic events ending with $\geq 70$ mg/dL: • 24-hour	Baseline, 0-4, 8-12, 22-26, 0-26 weeks, post-treatment period	Logistic regression with treatment, baseline HbA1c and baseline incidence for Level 2 hypoglycemia ending with $\geq 70$ mg/dL as covariates.

Endpoint	CGM Session*	Statistical Method
Duration of Level 1 or Level 2 hypoglycemic events: 
 
• 24-hour
 
	Baseline, 0-4, 8-12, 22-26, 0-26 weeks, post-treatment period	For 0-4, 8-12, 22-26 weeks: The MMRM model will include treatment, strata (country, routine use of personal CGM or FGM at randomization, baseline HbA1c stratum (<8.0%, ≥8.0%)), time and treatment-by-time interaction as fixed effects, and baseline duration as a covariate. For 0-26 weeks: ANCOVA model model will include treatment, strata (country, routine use of personal CGM or FGM at randomization, baseline HbA1c stratum (<8.0%, ≥8.0%)), and baseline duration. For Baseline and post-treatment period: ANOVA models only include treatment.
Duration of Level 2 hypoglycemic events: 
 
• 24-hour
 
	Baseline, 0-4, 8-12, 22-26, 0-26 weeks, post-treatment period.	Same models as for Level 1 or Level 2 hypoglycemic events. A listing will be provided for participants with Level 2 hypoglycemia episodes lasting >360 minutes
Duration of Level 2 hypoglycemic events ending with BG >=70 mg/dL: 
 
• 24-hour
 
	Baseline, 0-4, 8-12, 22-26, 0-26 weeks, post-treatment period.	Same models as for Level 1 or Level 2 hypoglycemic events.

Abbreviations: HbA1c = hemoglobin A1c.

Note: The hypoglycemic rate during defined period is a yearly rate and calculated by number of hypoglycemic events within the period/number of days patient at risk within the period\*365.25. The hypoglycemia incidence during defined period indicates if the patient has at least 1 hypoglycemic event within the period (Yes/No).

#### 4.6.2.3. Laboratory and Adverse Event for Hepatic Safety

Hepatic labs include

- alanine aminotransferase (ALT)
- aspartate aminotransferase (AST)
- total bilirubin (TBL)
- direct bilirubin (DBL)

- serum alkaline phosphatase (ALP), and
- gamma-glutamyltransferase (GGT).

When criteria are met for hepatic evaluations, investigators will conduct close monitoring of hepatic symptoms and liver tests, perform a comprehensive evaluation for alternative causes of abnormal liver tests, and complete follow-up hepatic safety CRFs.

The table below lists summary TFLs for the analysis of hepatic laboratory data.

Analysis	Details
Abnormal postbaseline categories – hepatic safety parameters	
ALT: The number and percentage of participants with a measurement greater than or equal to 1 time (1X), 3 times (3X), 5 times (5X), 10 times (10X), and 20 times (20X) the performing laboratory ULN during the postbaseline period will be summarized for all participants with a postbaseline value.
 
AST: The number and percentage of participants with a measurement greater than or equal to 1 time (1X), 3 times (3X), 5 times (5X), 10 times (10X), and 20 times (20X) the performing laboratory ULN during the postbaseline period will be summarized for all participants with a postbaseline value.
 
ALP: The number and percentage of participants with a measurement greater than or equal to 2 times (2X) and 3 times (3X) the performing laboratory ULN during the postbaseline period will be summarized for all participants with a postbaseline value.
 
TBL: The number and percentage of participants with a measurement greater than or equal to 2 times (2X), 5 times (5X), and 8 times (8X) the performing laboratory ULN during the postbaseline period will be summarized for all participants with a postbaseline value.
 
DBL: The number and percentage of participants with a measurement greater than or equal to 2 times (2X) and 5 times (5X) the performing laboratory ULN during the postbaseline period will be summarized for all participants with a postbaseline value.
 
GGT: The number and percentage of participants with a measurement greater than or equal to 2 times (2X) the performing laboratory ULN during the postbaseline period will be summarized for all participants with a postbaseline value.

Analysis	Details
Treatment-emergent potentially drug-related hepatic disorders	
Potentially drug-related hepatic disorders are defined using a custom query based on the following SMQs:
 
 
• Broad and narrow terms in the Liver-related investigations, signs and symptoms SMQ (20000008)
 
• Broad and narrow terms in the Cholestasis and jaundice of hepatic origin SMQ (20000009)
 
• Broad and narrow terms in the Hepatitis non-infections SMQ (20000010)
 
• Broad and narrow terms in the Hepatic failure, fibrosis and cirrhosis and other liver damage SMQ (20000013)
 
• Narrow terms in the Liver-related coagulation and bleeding disturbances SMQ (20000015)
 
 
These SMQs are a subset of the sub-SMQs comprising the full Hepatic Disorders SMQ. Only the sub-SMQs considered applicable to capturing potentially drug-related hepatic disorders are included.
 
The percentage of study participants with at least one of any of the MedDRA preferred terms from any of the above SMQs will be summarized in addition to the percentages for each MedDRA preferred term.

Hepatocellular drug-induced liver injury screening plot (TBL vs ALT or AST)	
Each participant's data is plotted based on their maximum postbaseline TBL (y-axis) and transaminase (ALT or AST, whichever is higher), regardless of the time between the 2 maximum values. Lines represent TBL and transaminase cutoffs of 2X ULN and 3X ULN, respectively. A potential Hy's law case is circled and is defined as having a maximum postbaseline TBL equal to or exceeding 2X ULN within 30 days after maximum postbaseline ALT or AST equal to or exceeding 3X ULN, without cholestasis (defined as ALP less than 2X ULN).

Hepatocellular drug-induced liver injury screening table	
The percentages of study participants falling in each of the 3 relevant quadrants of the plot (right upper, left upper, right lower) will be summarized in a table.

Cholestatic drug-induced liver injury screening plot (TBL vs ALP)	
Each participant's data is plotted based on their maximum postbaseline TBL (y-axis) and ALP (x-axis), regardless of the time between the 2 maximum values. Lines represent TBL and ALP cutoffs of 2X ULN and 3X ULN, respectively. A potential cholestatic liver injury case is circled and is defined as having a maximum postbaseline TBL equal to or exceeding 2X ULN within 30 days after maximum postbaseline ALP equal to or exceeding 3X ULN.

Cholestatic drug-induced liver injury screening table	
The percentages of study participants falling in each of the 3 relevant quadrants of the plot (right upper, left upper, right lower) will be summarized in a table.

List of Participants with potential hepatocellular drug-induced liver injury	
Includes participants falling in the right upper quadrant in the Hepatocellular Drug-Induced Liver Injury Screening plot.
 
Variables to include are unique subject ID, age, sex, race, treatment, max AST, max ALT, max ALP, max TBL.

Analysis	Details
List of Participants with potential cholestatic drug-induced liver injury	
Includes participants falling in the right upper quadrant in the Cholestatic Drug-Induced Liver Injury Screening plot.
 
Variables to include are unique subject identifier, age, sex, race, treatment, max AST, max ALT, max ALP, max TBL.

Abbreviations: ALP = alkaline phosphatase; ALT = alanine aminotransferase; AST = aspartate aminotransferase; CRF = case report form; DBL = direct bilirubin; GGT = gamma-glutamyl transferase; MedDRA = Medical Dictionary for Regulatory Activities; SMQ = Standardized MedDRA Query; TBL = total bilirubin; ULN = upper limit of normal.

Planned and unplanned measurements will be included. The measurements do not need to be taken at the same blood draw.

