### 8.2.5. Hepatic Monitoring

#### Close hepatic monitoring

##### *Initiating laboratory and clinical monitoring for abnormal liver laboratory test results*

Laboratory tests (Section 10.5), including ALT, AST, ALP, TBL, direct bilirubin, GGT, and creatine kinase, should be repeated within 48 to 72 hours to confirm the abnormality and to determine if it is increasing or decreasing, if 1 or more of these conditions occur.

If a participant with baseline results of...	develops the following elevations:
ALT or AST <1.5x ULN	ALT or AST $\geq$ 3x ULN
ALP <1.5x ULN	ALP $\geq$ 2x ULN
TBL <1.5x ULN	TBL $\geq$ 2x ULN (except for participants with Gilbert's syndrome)
ALT or AST $\geq$ 1.5x ULN	ALT or AST $\geq$ 2x baseline
ALP $\geq$ 1.5x ULN	ALP $\geq$ 2x baseline
TBL $\geq$ 1.5x ULN	TBL $\geq$ 1.5x baseline (except for participants with Gilbert's syndrome)

Abbreviations: ALP = alkaline phosphatase; ALT = alanine aminotransferase; AST = aspartate aminotransferase; TBL = total bilirubin; ULN = upper limit of normal.

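### The SAP circles a potential Hy's law case by comparing the dates of two maxima, so a qualifying transaminase and bilirubin pair within 30 days can be left uncircled on the screening plot

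*SAP*

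**What the plan says.** SAP 4.6.2.3 plans a hepatocellular screening plot with one point per participant: maximum postbaseline total bilirubin (TBL) against maximum "transaminase (ALT or AST, whichever is higher), regardless of the time between the 2 maximum values". Some points are circled as potential Hy's law cases. The circle requires "having a maximum postbaseline TBL equal to or exceeding 2X ULN within 30 days after maximum postbaseline ALT or AST", the transaminase being "equal to or exceeding 3X ULN, without cholestasis (defined as ALP less than 2X ULN").

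The cholestatic plot uses the parallel rule: "having a maximum postbaseline TBL equal to or exceeding 2X ULN within 30 days after maximum postbaseline ALP", with ALP at least 3X ULN.

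Two outputs back up the hepatocellular plot. A table gives the percentage of participants in each of three quadrants. A listing "Includes participants falling in the right upper quadrant in the Hepatocellular Drug-Induced Liver Injury Screening plot", and its content is fixed: "Variables to include are unique subject ID, age, sex, race, treatment, max AST, max ALT, max ALP, max TBL". The cholestatic plot has a matching table and listing. A note to the section adds: "Planned and unplanned measurements will be included. The measurements do not need to be taken at the same blood draw".

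Protocol 8.2.5 says that after a triggering liver abnormality the tests "should be repeated within 48 to 72 hours to confirm the abnormality". If the abnormality persists or worsens, monitoring starts at one to three times weekly. SAP 4.1 runs the analysis period for elevated laboratory values to the last visit, follow-up included.

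**The concern.** On the SAP's own thresholds, the event the circle is meant to mark is a bilirubin of at least 2X ULN arising soon after a transaminase of at least 3X ULN. The rule instead tests whether two maxima, each taken over the whole postbaseline period, fall in the right order and close enough together. These are different conditions. A participant whose liver tests are repeated often, over a period that extends into follow-up, can meet the first and fail the second.

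What is at stake is the labelling of a rare and important safety finding. In this section the circle is the only hepatic display that applies a timing criterion. The listing behind it holds maxima without dates, so a reader who sees an uncircled point in the right upper quadrant cannot tell from the listing whether the timing was met.

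**Working it through.** The documents give no event count, rate or power figure on this point, so there is no stated number to reproduce. The check applies the rule as written to constructed time courses. The courses are assumptions, not trial data, with ALP below 2X ULN throughout.

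**Inputs (SAP 4.6.2.3).** TBL at least 2X ULN; ALT or AST at least 3X ULN; window 0 to 30 days, counting the same day as day 0.

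**SAP rule.** Lag = day of maximum TBL − day of maximum ALT or AST; circled if 0 ≤ lag ≤ 30. The text does not say how ALT and AST combine, so three readings were tried:
- (i) either enzyme's maximum may qualify;
- (ii) only the higher of the two maxima counts;
- (iii) any TBL of at least 2X ULN in the 30 days after the transaminase maximum is enough.

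**Pairwise rule.** Circled if any ALT or AST of at least 3X ULN is followed within 0 to 30 days by any TBL of at least 2X ULN.

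| Course (multiples of ULN) | Lag of maxima (days) | (i) | (ii) | (iii) | Pairwise |
|---|---|---|---|---|---|
| A. ALT 6 and AST 4 day 84; TBL 2.5 day 98 | 98 − 84 = 14 | yes | yes | yes | yes |
| B. As A, then ALT 7 and AST 5 day 182 | 98 − 182 = −84 | no | no | no | yes |
| B2. As A, then ALT 5 and AST 3.5 day 182 | 98 − 84 = 14 | yes | yes | yes | yes |
| C. ALT 4 and AST 3.5 day 84; TBL 2.5 day 91; ALT 6, AST 5, TBL 2.2 day 98 | 91 − 98 = −7 | no | no | yes | yes |
| C2. AST maximum 5 day 84; TBL 2.5 day 91; ALT maximum 6 and TBL 2.2 day 98 | ALT 91 − 98 = −7; AST 91 − 84 = 7 | yes | no | yes | yes |
| D. ALT 8 and AST 6 day 30; ALT 4 day 84; TBL 2.5 day 98 | 98 − 30 = 68 | no | no | no | yes |
| E. ALT 4 day 14; TBL 2.5 day 182 | 182 − 14 = 168 | no | no | no | no |

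Six courses contain a qualifying pair (A to D) and one does not (E). The pairwise rule circles all six and leaves E alone.

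Courses B and D go uncircled on every reading. In B the day 84 and day 98 values still form a pair 14 days apart, but a later, higher peak has taken over as the maximum. In D the day 84 transaminase is 14 days before the bilirubin maximum, but an earlier, higher value sits outside the window. B2 shows that a second peak matters only if it exceeds the first. C and C2 depend on which reading is programmed.

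**Direction of error.** If the two maxima satisfy the SAP rule, they are themselves a transaminase of at least 3X ULN and a TBL of at least 2X ULN within 30 days, so the pairwise rule is also met. With the ALP condition applied identically, the SAP's circled set is a subset of the pairwise set: it can miss cases but cannot add any.

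**What still captures them.** All seven courses have TBL of at least 2X and a transaminase of at least 3X, so all fall in the right upper quadrant and appear in its table and listing.

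**The case against.** The strongest reply is that the circle decides little. The table counts quadrants and the listing takes everyone in the right upper quadrant, so neither depends on timing and neither loses a case. The SAP plans no count of circled cases, so a reader who infers that a reported number of Hy's law cases would be wrong goes beyond the documents. Nor would such a participant escape review. Protocol 7.1.1 has a combined transaminase and bilirubin criterion with no condition on the order of peaks. Protocol 8.2.5 calls for comprehensive evaluation and hepatic safety data collection on bilirubin alone, subject to baseline level and Gilbert's syndrome. The data monitoring committee sees unblinded safety data. All of this stands.

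A reader might also infer that the 48 to 72 hour repeat test makes the failure likely. The documents do not support that. Take ALT 4X and TBL 2.2X on one day, then ALT 6X at the repeat. The circle is lost only if TBL does not rise at the repeat or reach a later maximum within 30 days of the ALT maximum. The protocol repeats bilirubin along with the transaminases; if both rise, the maxima share a date and the case is circled. An AST maximum before the bilirubin maximum could also rescue it on reading (i).

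Two further replies carry some weight. The pairwise rule is also one-directional, so it is not a complete definition. And SAP section 1 places figure and listing specifications in separate documents, not available here, which might clarify the programming.

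These replies limit the consequence but do not remove the defect. The SAP states a rule, nothing in 4.6.2.3 widens it to other pairs, and the note on separate blood draws does not change which values are compared. The listing cannot repair it without dates. The dated abnormal-laboratory listing in SAP 4.6.2.4 relies on Appendix 10, which has no ALT, AST, ALP or bilirubin rows and refers to sponsor-defined liver categories not given there, so it is unclear that it fills the gap.

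**Conclusion.** The point holds as a minor defect in a safety display. As written, the circle can be missing from a participant who has a qualifying pair within 30 days, and the cholestatic circle shares the construction. The error is an omission only, provided ALP is treated the same way under both rules; the SAP gives no date for the ALP condition.

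The size is a missing circle around a point that is still plotted, tabulated and listed. How often this would happen cannot be judged from the documents. Efficacy, type I error, power and protocol hepatic management are untouched. The documents do not support the stronger conclusion that a liver safety signal would be lost.

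The conclusion rests on reading the SAP sentence literally. Courses B and D fail on all three readings tried; the failure when the transaminase peaks after bilirubin depends on the reading and on the bilirubin values that follow.

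**What to change.** Keep the plot axes as maxima. Define the Hy's law circle on any postbaseline ALT or AST of at least 3X ULN with any postbaseline TBL of at least 2X ULN on the same day or within 30 days after it. State the date at which the existing ALP condition is assessed. Apply the same pairwise construction to the cholestatic circle, using ALP of at least 3X ULN. Add the relevant dates and the flag itself to both drug-induced liver injury listings, so that the timing can be checked for any point in the right upper quadrant.

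The cost is a sentence or two of SAP text for each circle, a pairwise date check in the derivation, extra listing columns, and possibly one or two more circled cases to review. That last figure is a judgement; the documents give no rate.

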#### 4.6.2.4. Clinical Laboratory Evaluations

For the following selected laboratory measures:

- Liver enzyme tests: ALT, ALP, AST, GGT, DBL and Total Bilirubin
- Lipid measures: Triglycerides, total cholesterol, LDL-C, and HDL-C (results from fasting samples) )

MMRM model (as described in Section 4.6) will be used for the observed values, change from baseline and percentage change from baseline, for which log-transformation will be applied. Geometric LS means will be provided. Analyses will be provided in both international units (SI) and conventional units (CN) if they are different.

Box plots with descriptive statistics for the observed values and change from baseline will be provided by treatment group and visit.

For other laboratory measures, descriptive summaries will be provided for the observed values and change from baseline by treatment group and visit.

The percentages of participants with elevated or low values meeting specified levels (see Appendix 10, Section 6.10) at any time post-baseline (including scheduled and unscheduled measurements) will be summarized and compared between treatment groups using risk difference and 95% confidence interval.

A listing of abnormal laboratory analytes collected quantitatively (high or low during postbaseline period using Level 2 definitions in Appendix 10) and qualitatively (abnormal during postbaseline period) will be provided, including participant identification, treatment group, laboratory sample collection day (that is, days from start of study drug), analyte name, abnormal result, and reference low or high limits (Level 2 cut-off value).

Scatter plots of maximum-by-maximum measurements and minimum-by-minimum measurements will not be created a-priori. They may be created if warranted after review of the planned tables and figures, using Figures 6.3 and 6.4 from the Analysis and Displays for Labs white paper (PHUSE 2022) as the model. ADaM datasets will include variables to enable the creation of scatter plots for use in either an interactive tool or for ad-hoc figures.

#### 4.6.2.5. Vital Signs and Physical Characteristics

The planned summaries are provided in the Table below. The measurements analyzed for vital signs and physical characteristics include systolic BP, diastolic BP, pulse, weight, and BMI.

Analysis Type	Analysis Details
Observed values change by visit	
 
Includes all participants in the safety population who have both a baseline and at least 1 postbaseline observation
 
MMRM model (as described in Section 4.6) will be used.
 
 
See also: Table 6.2 from the Analyses and Displays for Labs white paper (PHUSE 2022)

Summary by category	
 
Definitions provided in Tables 31-33 from FDA's September 2022 Standard Safety Tables and Figures document will be used for the numerator. 
 
Systolic BP (mm Hg): 
 
Low: Level 1: <90
 
High: Level 1: <math>\geq 90</math>, Level 2: <math>\geq 120</math>, Level 3: <math>\geq 140</math>, Level 4: <math>\geq 160</math>, Level 5: <math>\geq 180</math>
 
 
 
Diastolic BP (mm Hg): 
 
Low: Level 1: <60
 
High: Level 1: <math>\geq 60</math>, Level 2: <math>\geq 90</math>, Level 3: <math>\geq 110</math>, Level 4: <math>\geq 120</math>
 
 
 
 
 
Includes participants with at least one postbaseline measurement.
 
Statistical comparisons (using methods described in Section 4.6) will be included.
 

Participants meeting CTC grade changes in weight	
For weight, cutoffs informed by CTCAE version 5 (Grades 1-3) will be used:
 
 
(Loss) decrease: Level 1: <math>\geq 5\%</math>, Level 2: <math>\geq 10\%</math>, Level 3: <math>\geq 20\%</math>
 
(Gain) increase: Level 1: <math>\geq 5\%</math>, Level 2: <math>\geq 10\%</math>, Level 3: <math>\geq 20\%</math>
 
 
Includes participants with both a baseline and at least 1 postbaseline observation.
 
 
Statistical comparisons (using methods described in Section 4.6) will be included.
 

